**APPENDIX A: DSM REPORTING TABLE FOR ADVERSE EVENTS**

Expected Risks	Number	Frequency

 
Renal injury/failure (reported with systemic administration, never reported with EBUS-TBNI delivery)
 
		

 
Myelosuppression (reported with systemic administration, never reported with EBUS-TBNI delivery)
 
		

 
Neurologic side effects, including hearing impairment (reported with systemic administration, never reported with EBUS-TBNI delivery)
 
		

 
Hepatic injury (reported with systemic administration, never reported with EBUS-TBNI delivery)
 
		

 
Nausea/vomiting (known but rare adverse event with EBUS-TBNI cisplatin)
 
		

 
Significant bleeding (defined as >100mL is rarely reported with EBUS for biopsies <0.1%, never for EBUS-TBNI)
 
		

**APPENDIX B:****NCI COMMON ADVERSE EVENTS FOR COMMONLY USED ONCOLOGY DRUGS (CAEPR)****Possible Side Effects of Cisplatin (Table Version Date: November 8, 2019)****COMMON, SOME MAY BE SERIOUS**

In 100 people receiving Cisplatin, more than 20 and up to 100 may have:

- Infection, especially when white blood cell count is low
- Bruising, bleeding
- Anemia which may cause tiredness, or may require blood transfusions
- Kidney damage which may cause swelling, may require dialysis
- Hearing loss including ringing in the ears
- Nausea, vomiting
- Confusion
- Numbness and tingling of the arms and legs

**OCCASIONAL, SOME MAY BE SERIOUS**

In 100 people receiving Cisplatin, from 4 to 20 may have:

- Diarrhea
- Change in taste
- Allergic reaction which may cause rash, low blood pressure, wheezing, shortness of breath, swelling of the face or throat
- Hair loss

**RARE, AND SERIOUS**

In 100 people receiving Cisplatin, 3 or fewer may have:

- Brain damage, Posterior Reversible Encephalopathy syndrome, which may cause headache, seizure, blindness
- Seizure
- A new cancer resulting from treatment of a prior cancer

## APPENDIX C:

## SCRIPT FOR IDENTIFICATION OF ADVERSE EVENTS BASED ON NCI CAEPR

The [name].  
College of Medicine

THE UNIVERSITY OF VERMONT

**A PHASE I TRIAL OF INTRATUMORAL CISPLATIN DELIVERED AT DIAGNOSIS FOR  
EARLY STAGE, RESECTABLE, NON-SMALL CELL LUNG CANCER**

**SUBJECT NO.** \_\_\_\_\_ **SUBJECT INITIALS** \_\_\_\_\_

Follow up contact- 1 week post bronchoscopy \_\_\_\_\_ / \_\_\_\_\_ / \_\_\_\_\_  
Date

Did the subject report any adverse events?  Yes  No

1. Do you have any health concerns since we saw you on the day of the procedure?

2. Since the procedure, have you had:

Wheezing or shortness of breath?

Chest pain?

Fever or rash?

Easy bruising or bleeding?

Itching?

Hearing loss or ringing in your ears?

Nausea or vomiting?

Confusion?

Numbness or tingling in the arms or legs/

Diarrhea?

Change in taste?

Swelling of the face or throat?

Headache?

Seizure?

**Followup Contact Conducted by:** \_\_\_\_\_ / \_\_\_\_\_ / \_\_\_\_\_

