#### **4.3. Treatments and Evaluations by Visit:**

##### **4.3.1. Screening Evaluation:**

4.3.1.1. Initial evaluation performed via face-to-face visit or televideo (standard of care)

4.3.1.2. A non-contrast chest CT scan will be performed within 30 days of the screening visit.

4.3.1.3. Baseline blood draws within 14 days of bronchoscopy:

4.3.1.3.1. Samples for the following laboratory tests will be sent if not available:

4.3.1.3.1.1. Hematology Panel: WBC count, RBC count, hemoglobin, hematocrit, platelet count, differential count (neutrophils, eosinophils, basophils, monocytes, lymphocytes, other cells)

4.3.1.3.1.2. Chemistry Panel (serum or plasma): sodium, potassium, chloride, bicarbonate, glucose, creatinine, albumin (pre-op only), calcium, magnesium

4.3.1.3.1.3. Liver panel: ALT, AST, INR, alkaline phosphatase, bilirubin

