4.3.2.20. A follow up CXR will be performed (standard of care)

**4.3.3. 24H Post-Bronchoscopy Evaluation**

4.3.3.1. A follow up telephone/televideo or in-person evaluation will be performed by a physician, advanced practice practitioner, or nurse and will occur within 36 hours of completion of the procedure. A standard script (Appendix) will be used to assess for AEs. (research)

4.3.3.2. Blood will be drawn for an additional platinum level for patients able to return for an in-person visit.(research)

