**4.3.4. 1 Week Post-Bronchoscopy Follow Up**

4.3.4.1. Participants will undergo an evaluation by a physician or advanced practice provider between 5-9 days post-procedure. Visit will occur in-person. The only exception would be COVID related issues. In that case, telemedicine and local labs will be allowed. No phone evaluations will occur unless there is no other option. A standard script will be used to assess for AEs. (research)

4.3.4.2. A blood draw to assess for AEs will be performed between 5-9 days post-procedure.(research)

4.3.4.2.1. Samples for the following laboratory tests will be sent to UVMMC laboratories for analysis:

- 4.3.4.2.1.1. Hematology Panel
- 4.3.4.2.1.2. Chemistry Panel
- 4.3.4.2.1.3. Liver Panel

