## 7.2. Adverse Events:

7.2.1. Definition of adverse events (AE) for this study:

7.2.1.1. An adverse event (AE) will be considered any undesirable sign, symptom or medical or psychological condition even if the event is not considered to be related to the investigational drug/device/intervention. Medical conditions/diseases present before starting the investigational drug/intervention will be considered AEs only if they worsen after starting study treatment/intervention. An AE is also any undesirable and unintended effect of research occurring in human subjects as a result of the collection of identifiable

private information under the research. AEs also include any problems associated with the use of an investigational device that adversely affects the rights, safety or welfare of subjects.

7.2.2. Define of serious adverse events (SAEs):

7.2.2.1. A serious adverse event (SAE) will be considered any undesirable sign, symptom, or medical condition which is fatal, life-threatening, requires or prolongs inpatient hospitalization, results in persistent or significant disability/incapacity, constitutes a congenital anomaly/ birth defect, is medically significant and which the investigator regards as serious based on appropriate medical judgment. An important medical event is any AE that may not result in death, be life-threatening, or require hospitalization but may be considered an SAE when, based upon appropriate medical judgment, it may jeopardize the patient and may require medical or surgical intervention to prevent one of the outcomes listed in the definitions of SAEs.

7.2.2.2. Any serious psychological and emotional distress resulting from study participation (suggesting need for professional counseling or intervention).

7.2.3. ALL AEs above will be collected/ recorded.

7.2.4. A REDCap database will be used to save and manage data.

7.2.4.1. The database is located on the secure UVM server and is firewall protected. Data will be collected from source documents including but not limited to clinic notes, laboratory results, and other EMR available documents. The PI will review all AE data at the end of the study period for each patient. Data will be entered and managed by trained study personnel.

7.2.5. AEs be classified/graded using NCI Common Toxicity Criteria for Adverse Events (CTCAE), Version 5.0

7.2.6. The PI will determine the relationship of AEs to the study using the following scale:

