7.2.6.1. Definite: AE is clearly related in time and a direct association can be demonstrated to the study intervention.

7.2.6.2. Probable: AE is reasonably related in time and is more likely explained by the study intervention than by other causes.

7.2.6.3. Possible: AE may be reasonably related in time and the AE can be explained equally well by causes other than the study intervention.

7.2.6.4. Unlikely: A potential relationship could exist with the study intervention, but the AE is most likely explained by other causes.

7.2.6.5. Unrelated:AE is clearly not related to intervention and can be fully explained by another cause. This other cause should be provided.

7.2.7. Recording/reporting of baseline AEs will begin after the subject signs consent. Subsequent AEs will be recorded following initiation of the bronchoscopic procedure.

7.2.8. Recording/reporting of AEs will end following surgical resection or 30 days after cisplatin delivery, whichever occurs first.

7.2.9. The PI will review all AEs following the 1 week follow up visit (occurs at 5-9 days performed by a physician or advanced practice provider), both to assess for unexpected and serious AEs and to ensure that dose escalation occurs consistent with the statistical plan.

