9.8. This aggregate review will occur quarterly

**1. TABLE OF STUDY VISITS AND PROCEDURES:**

	Screening	Phase 1: Intratumoral Cisplatin Protocol					
		Pre-Bronchoscopy	Bronchoscopic Procedure	24H Followup	1 Week Followup	2 Week Followup	Surgical Resection**
Study Visit							
Informed Consent	X						
History and Evaluation	X			X	X	X	
Research Biopsies			X				
Delivery of Cisplatin			X				
Cisplatin Blood Levels			X	X	X		
CXR	X (pre-bronchoscopy if no imaging within prior 7 days)		X (post-procedure)				
24H Post-Procedure Follow Up				X			
Hematology Panel	X				X	X	
Chemistry Panel	X				X	X	
Liver Panel	X				X	X	
Albumin	X						
Blood Draw for Research			X				X (day of resection)
Review of Adverse Events and Concomitant Medications				X	X	X	
Chest CT Scan (non-contrast if not performed or inadequate will be ordered for research purposes)	X					X	
Obtain Research Resected Pathology Specimen							X (fresh and fixed)

\* Research biopsies will be evaluated for changes in immunocellular infiltrate vs. resection specimen

\*\*Surgical resection to occur 14-30 days post-procedure

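### The symptom script is given only after injection and has no matching graded baseline, so existing symptoms that the baseline history misses may be tabulated as post-cisplatin adverse events

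*Combined protocol and SAP*

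**What the plan says.** **After injection.** Section 4.3.3.1 (24-hour contact) states: "A standard script (Appendix) will be used to assess for AEs". Sections 4.3.4.1 and 4.3.5.1 call for a standard script at 1 week and 2 weeks. The form in Appendix C is labelled "Follow up contact- 1 week post bronchoscopy". After one open question on health concerns it lists 14 symptom items under "Since the procedure, have you had". In the Table of Study Visits and Procedures, the row "Review of Adverse Events and Concomitant Medications" is marked at the 24-hour, 1-week and 2-week contacts only.

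**Before injection.** Section 7.2.7 states: "Recording/reporting of baseline AEs will begin after the subject signs consent". The visit table marks a history and evaluation at screening, which 4.3.1.1 describes as standard of care. Section 3.1.7 requires a surgeon to review past history, medications, lung function tests and CT. None of these sections names a symptom list or asks for a CTCAE grade for symptoms.

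**The comparison rule.** Under 7.2.1.1, conditions present before treatment "will be considered AEs only if they worsen after starting study treatment/intervention".

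**The concern.** The worsening rule in 7.2.1.1 needs a before and an after for each symptom. The after is obtained by direct questions on a fixed list. The plan does not say how the before is obtained. A direct question can bring out mild tingling or ringing in the ears that a general history leaves unrecorded. The script also asks whether a symptom has been present since the procedure, not whether it is new or worse, so a patient with long-standing breathlessness or tinnitus can truthfully answer yes.

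The safety profile (6.2.2.1) and the adverse event tables by dose tier (6.5.1) could then include symptoms that were there before cisplatin. The trial has no control arm to show the background rate and plans about 10 to 12 patients (6.3). Section 7.1 describes hearing and other neurologic effects as never reported with intratumoral delivery, so even one misclassified case would stand out as an apparent new signal.

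**Working it through.** The point concerns how data are collected, and the plan states no figure on it to reproduce. The check sets the sections side by side.

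1. **Where the script is used.** Post-injection contacts with the script: 24 hours, 1 week and 2 weeks, so 3 of 3. Pre-injection contacts (screening, pre-bronchoscopy) for which a script is specified: none.

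2. **What the script asks.** The 14 items cover wheeze or breathlessness, chest pain, fever or rash, bruising or bleeding, itching, hearing loss or tinnitus, nausea or vomiting, confusion, numbness or tingling, diarrhoea, taste change, face or throat swelling, headache and seizure. None asks about onset or change.

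3. **How laboratory values are treated.** Haematology, chemistry and liver panels are obtained at baseline (4.3.1.3) and repeated at 1 and 2 weeks (4.3.4.2, 4.3.5.2). Section 6.2.1.3.7 judges laboratory events by change from baseline. The plan thus provides a structured baseline for laboratory values but not for symptoms.

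4. **What one misclassified patient does to a tier.** With 3 patients in a tier, 1/3 = 33 percentage points. With 6, 1/6 = 17 points.

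5. **Illustration only.** Let p be the share of patients who have a given symptom before injection, whose baseline misses it, and in whom it is then recorded as new. The expected number is n × p, and the chance of at least one is 1 − (1 − p)^n. No document gives p; the values below are assumptions.

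| p (assumed) | n = 10: expected; chance of at least one | n = 12: expected; chance of at least one |
|---|---|---|
| 5% | 0.5; 40% | 0.6; 46% |
| 10% | 1.0; 65% | 1.2; 72% |
| 20% | 2.0; 89% | 2.4; 93% |
| 40% | 4.0; 99% | 4.8; 99.8% |

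The upper rows are not credible for items such as seizure or confusion.

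6. **Reach into the dose decision.** A DLT needs grade 3 or above (6.2.1.1), and entry is limited to ECOG 0 or 1 (3.1.2), so a missed baseline symptom that would count as a DLT should be rare. Let t be the true DLT rate per patient, s the rate of spurious DLTs, and q = 1 − (1 − t)(1 − s). The chance of escalating from a dose level under 4.1.10 is (1 − q)^3 + 3q(1 − q)^5. Assuming t = 10%, it is 0.906 at s = 0, 0.891 at s = 1%, 0.875 at s = 2% and 0.824 at s = 5%. For small s the change is small. It is not zero in principle, because 6.2.1.1 attaches no attribution or change-from-baseline condition to the DLT definition.

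**The case against.** The strongest reply is that the plan already has a baseline. Adverse events are recorded from consent, a history is taken at screening, a surgeon reviews the patient's history and medications, and pre-existing conditions are excluded unless they worsen. A physician or advanced practice provider sees the patient at 1 and 2 weeks and can ask when a symptom began, and the script is anchored to the time since the procedure. The investigator also assigns each event one of five levels of attribution, including unlikely and unrelated (7.2.6). Section 6.5.1 plans no before-and-after comparison, and every tier gets the same script at the same times, so the method does not by itself favour one tier.

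Much of this stands, and it rules out stronger readings that a reader might infer:

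- That existing symptoms will as a rule first appear as post-cisplatin events. Sections 7.2.7 and 7.2.1.1 contradict that.
- That the baseline is unprompted. The documents do not say how baseline events are elicited, and the protocol does not reproduce the case report forms. What can be said is that no prompted or graded symptom baseline is specified.
- That these symptoms could not be told apart from drug toxicity. A missing baseline grade weakens the attribution judgement but does not remove it.

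The reply does not close the gap. Neither the worsening rule nor attribution can reliably correct for a symptom the baseline never recorded, and the follow-up wording does not ask about change.

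**Conclusion.** The point holds as a gap in symptom ascertainment. The prompted list is scheduled only after injection, no matching graded baseline is specified, and the rule that excludes unchanged pre-existing conditions depends on one. Symptoms that the consent-stage recording and screening history miss may therefore enter the tables as post-cisplatin events.

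The consequence is mainly some possible overstatement of low-grade toxicity in a small, uncontrolled safety table. Little effect on DLT or the MTD is expected, given the grade 3 threshold and the performance status limit. No size can be derived from the documents: the probabilities in the working follow from assumed values of p and are not estimates of this trial's error. The conclusion assumes that the baseline case report form does not already contain an equivalent graded symptom list. If it does, the protocol needs only to say so and to correct the follow-up wording.

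**What to change.** - Give the Appendix C symptom list once between consent and bronchoscopy, asking about current symptoms, with a CTCAE v5.0 grade for each positive answer. Screening or the pre-bronchoscopy contact would serve.
- Mark the adverse event review row of the visit table in that column.
- Reword the lead-in of the follow-up script so that it asks for symptoms that are new or worse since the procedure.
- Add to 6.5.1 that a prompted symptom counts as treatment-emergent only if it is new or of higher grade than this baseline. This turns the general rule in 7.2.1.1 into a tabulation rule.

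The cost is a few minutes at a visit that already takes place, one more CRF page, one mark in the visit table and one sentence in 6.5.1. Some consented patients who are then not injected, for example because ROSE is non-diagnostic, will have completed the form without need. No procedure is added. A baseline that was not taken cannot be reliably reconstructed later.
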